6.3. Analysis of safety

6.3.1. Analysis of safety planned in the protocol

The safety analysis will be performed on the ES for safety and will include the analysis of the following categories of events:

- Serious Adverse Events (SAEs)
- pIMDs

All SAEs and pIMDs occurring at any time during the study will be recorded according to the protocol-specified reporting rules.

The verbatim reports of the symptoms will be reviewed by a physician and the signs and symptoms will be coded according to the MedDRA Dictionary for Adverse Reaction Terminology. Every verbatim term will be matched with the appropriate preferred term (PT). The number and the percentage of subjects who experienced at least one SAE with its exact 95% CI will be tabulated by group and by MedDRA PT. Same tabulation will be performed for subjects who experienced any pIMDs.

For the corresponding percentages, the denominator will be the respective numbers of exposed subjects.

SAEs or pIMDs related to the investigational vaccine administered in NTHI-Mcat-001 study, which were reported after last subject last visit of study NTHI-Mcat-001 and AFTER the subject signed the Informed Consent Form of NTHI-MCAT-006, have to be reported and included in the analyses of NTHI-MCAT-006 study.

The number of subjects who experienced any **SAE related to study participation or concurrent GSK medication/ vaccination**, from first visit up to study conclusion will be reported.

Deaths, and withdrawal due to SAE(s) reported during the entire study will be tabulated.

6.3.1.1. Concomitant Medication

Medications will be coded using the GSKDRUG dictionary.

The frequencies and percentages of subjects starting/reporting concomitant medications within the entire study period will be tabulated by group. A concomitant medications categorization will result from listings review meetings and will be considered in the summaries.

CONFIDENTIAL204913 (NTHI-MCAT-006 EXT:001)
Statistical Analysis Plan Final

7. ANALYSIS INTERPRETATION

All analyses are descriptive. The use of these descriptive analyses should be limited to supportive analysis of confirmatory analyses or hypothesis generation.

8. CONDUCT OF ANALYSES

8.1. Sequence of analyses

Table 2 Sequence of Analysis

Description	Analysis ID	Disclosure Purpose (CTRS=public posting, SR=study report, internal)	Study Headline Summary (SHS)requiring expedited communication to upper management (Yes/No)
Interim 1	E1_02	Internal	No
Interim 2	E1_03	Internal	No
Interim 3	E1_04	Internal	No
Final Analysis	E1_01	CTRS & Study report	Yes

8.2. Statistical considerations for interim analyses

Three interim analyses will be performed on all data obtained up to Month 20, Month 26 and Month 38, respectively. The study may be stopped if the GMC ratio (point estimate; Active [10-10-10-AS and 10-10-3-AS groups] versus PLACE2) for at least 2 out of 4 antigens is ≤ 2 , conclusion of further blood draws and early stop of the trial may be considered. Therefore, 2 GMC ratios per antigen will be calculated: 10-10-10-AS versus PLACE2, and 10-10-3-AS versus PLACE2.

- The analysis of data up to Visit 1 (Month 20) will be performed in a first step for Interim 1. This analysis will include:
 - The analysis of primary objective, as described in the section [6](#) of this document, based on the analysis of humoral immunogenicity results up to six months (Month 20) following last study visit in NTHI-Mcat-001.
 - The analysis of secondary objective, as described in the section [6](#) of this document, based on safety data collected between last visit in parent study NTHI-Mcat-001 (Month 14) and up to Visit 1 (Month 20).

This analysis will be performed on cleaned data and will be reviewed internally only. Individual listing will be provided at this stage.

If the data of the NTHI-MCAT 001 study will not be available and cleaned (freezed), an ANOVA model with only group as independent variable will be fitted instead of the planned ANCOVA model to estimate GMR between groups and placebo.

CONFIDENTIAL204913 (NTHI-MCAT-006 EXT:001)
Statistical Analysis Plan Final

- The analysis of data up to Visit 2 (Month 26) will be performed in a second step for Interim 2. This analysis will include:
 - The analysis of primary objective, as described in the section [6](#) of this document, based on the analysis of humoral immunogenicity results up to one year (Month 26) following last study visit in NTHi-Mcat-001 study.
 - The analysis of secondary objective, as described in the section [6](#) of this document, based on safety data collected between last visit in parent study NTHi-Mcat-001 (Month 14) and up to Visit 2 (Month 26).

This analysis will be performed on cleaned data and will be reviewed internally only. Individual listing will be provided at this stage.

- The analysis of data up to Visit 4 (Month 38) will be performed in a third step for Interim 3. This analysis will include:
 - The analysis of primary objective, as described in the section [6](#) of this document, based on the analysis of humoral immunogenicity results up to one year (Month 26) following last study visit in NTHi-Mcat-001 study.
 - The analysis of secondary objective, as described in the section [6](#) of this document, based on safety data collected between last visit in parent study NTHi-Mcat-001 (Month 14) and up to Visit 4 (Month 38).

This analysis will be performed on cleaned data and will be reviewed internally only. Individual listing will be provided at this stage.

- The analysis of data up to study end will be performed in a final step for Final Analysis. This analysis will include:
 - The analysis of primary objective, as described in the section [6](#) of this document, based on immunogenicity results of each study visit.
 - The analysis of secondary objective, as described in the section [6](#) of this document, based on safety data collected between last visit in parent study NTHi-Mcat-001 (Month 14) and up to study end.

This analysis will be performed on cleaned data and be documented in a statistical report. Individual listing will be provided at this stage.

CONFIDENTIAL204913 (NTHI-MCAT-006 EXT:001)
Statistical Analysis Plan Final**9. CHANGES FROM PLANNED ANALYSES**

Not Applicable.

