## 5.5. Outline of study procedures

**Table 2 List of study procedures**

Epoch	Epoch 001					
	Visit 1	Visit 2	Visit 3	Visit 4	Visit 5	Visit 6
Type of contact						
Timepoints 	Month 20	Month 26	Month 32	Month 38	Month 44	Month 50
Sampling timepoints	Follow-up Y1		Follow-up Y2		Follow-up Y3	
Informed consent	●					
Check inclusion/exclusion criteria	●					
Collect demographic data	●					
Medical history	●					
Physical examination	● 	○ 				
Laboratory assays						
Blood sampling for antibody determination and assay validation/development (~20 ml)	●	●	●	●	●	●
Safety assessment						
Record any concomitant medications/vaccinations 	●	●	●	●	●	●
Record any intercurrent medical conditions 	●	●	●	●	●	●
Recording of any pIMDs	●	●	●	●	●	●
Recording of SAEs	●	●	●	●	●	●
Study Conclusion						●

Note: The double-line borders following Month 20, Month 26 and Month 38 indicate the analyses which will be performed on all data obtained up to Month 20, Month 26 and Month 38, respectively. The study may be stopped if the stopping guidelines indicated in section 10.9.2 are met.

Y = year; pIMD = potential immune mediated diseases; SAE = serious adverse events.

- is used to indicate a study procedure that requires documentation in the individual eCRF.
- is used to indicate a study procedure that does not require documentation in the individual eCRF.

 Timepoints are indicated starting from dose 1 vaccination in NTHi-Mcat-001 study.

 Concomitant medication/products/vaccination as indicated in Section 6.1.1 need to be recorded.

 Complete physical examination including vital signs (systolic/diastolic blood pressure, heart rate and respiratory rate after at least 10 minutes of rest)

 Symptom directed physical examination.

 Medical conditions that, by potentially altering the immune response of a subject (except pregnancies), may lead to a subject being eliminated from analysis.

**CONFIDENTIAL**204913 (NTHI-MCAT-006 EXT:001)  
Protocol Amendment 1 Final

The investigator must arrange study visits within the interval provided in [Table 3](#).

**Table 3** Intervals between study visits (Amended 28 June 2018)

Interval 	Optimal length of interval 	Allowed interval
Visit 1 (Month 20) → Visit 2 (Month 26)	6 calendar months after Visit 1 NTHI MCAT 006	±20 elapsed days from optimal planned visit day

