**10.9.1. Sequence of analyses**

In this study, three interim analyses (at Visit 1, Visit 1 to Visit 2 and Visit 1 to Visit 4) and one final, cumulative analyses (Visit 1 to Visit 6) will be performed on all subjects:

- The analysis of data at Visit 1 (Month 20) will be performed in a first step. This analysis will include:
  - The analysis of humoral immunogenicity results up to six months (Month 20) following last study visit in NTHi-Mcat-001 study on cleaned data.

This analysis will be documented in a statistical report. Individual listings will be provided at this stage.

- The analysis of data from Visit 1 (Month 20) up to Visit 2 (Month 26) will be performed in a second step. This analysis will include:
  - The analysis of humoral immunogenicity results up to one year (Month 26) following last study visit in NTHi-Mcat-001 study and
  - SAEs and pIMDs up to one year (Month 26) following last study visit in NTHi-Mcat-001 on cleaned data.

This analysis will be documented in a statistical report. Individual listings will be provided at this stage.

- The analysis of data from Visit 1 (Month 20) up to Visit 4 (Month 38) will be performed in a third step. This analysis will include:
  - The analysis of humoral immunogenicity results up to two years (Month 38) following last study visit in NTHi-Mcat-001 study and
  - SAEs and pIMDs up to two years (Month 38) following last study visit in NTHi-Mcat-001 study on cleaned data.

This analysis will be documented in a statistical report. Individual listings will be provided at this stage.

- The analysis from Visit 1 (Month 20) up to Visit 6 (Month 50) will be performed in a fourth step. This analysis will include:
  - The final analysis of all immunogenicity results up to three years (Month 50) following last study visit in NTHi-Mcat-001 study.
  - SAEs and pIMDs up to three years (Month 50) following last study visit on cleaned data.

In addition, all previous analyses will be re-produced based on cleaned data. The final study report will be written only at this point. Individual listings will be provided.

**CONFIDENTIAL**204913 (NTHI-MCAT-006 EXT:001)  
Protocol Amendment 1 Final

An integrated clinical study report containing all data will be written and made available to the investigators.

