**10.9.1. Sequence of analyses**

*Refer to Table 3 for intervals between study visits detailed information.*

**Appendix A LABORATORY ASSAYS***Anti-PE antibodies*

Anti-PE antibodies will be determined using an ELISA assay developed by GSK Biologicals. Concentration of specific anti-PE antibodies will be determined, using in-house made reference serum. The technical cut-off of the assay is **825 EU/mL**.

*Anti-PilA antibodies*

Anti-PilA antibodies will be determined using an ELISA assay developed by GSK Biologicals. Concentration of specific anti-PilA antibodies will be determined, using an in-house made reference serum. The technical cut-off of the assay is **716 EU/mL**.

*Anti-UspA2 antibodies*

Anti-UspA2 antibodies will be determined using an ELISA assay developed by GSK Biologicals. Concentration of specific anti-UspA2 antibodies will be determined, using an in-house made reference serum. The technical cut-off of the assay is **4838 EU/mL**.

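### SAP 8.2 stops the Interim 3 antibody data at Month 26, although the rest of that section and the protocol put this look at Month 38

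*SAP*

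**What the plan says.** SAP 8.2 opens by fixing the three looks: "Three interim analyses will be performed on all data obtained up to Month 20, Month 26 and Month 38, respectively". It introduces the third with "The analysis of data up to Visit 4 (Month 38) will be performed in a third step for Interim 3". The first bullet under that lead-in, which covers the primary objective, then describes the analysis as "based on the analysis of humoral immunogenicity results up to one year (Month 26) following last study visit in NTHi-Mcat-001 study". The next bullet takes the safety data for the same look to Visit 4 (Month 38).

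The protocol is consistent on this look:

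- The note to Table 2 (section 5.5) refers to "analyses which will be performed on all data obtained up to Month 20, Month 26 and Month 38, respectively".
- Section 10.6 gives the same three months.
- Section 10.9.1 describes the third step as "The analysis of humoral immunogenicity results up to two years (Month 38) following last study visit in NTHi-Mcat-001 study".
- Section 10.9.2 requires the primary objective to be evaluated, and the stopping guideline based on geometric mean concentration (GMC) ratios to be applied, at every interim.

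**The concern.** The bullet defines which primary-endpoint data enter the last look before the final analysis. As written, it gives Interim 3 the same immunogenicity cut-off as Interim 2, a year earlier than the look it belongs to. Someone programming from that line alone would repeat the Interim 2 antibody analysis and leave out the Month 32 and Month 38 results. The active-versus-placebo GMC ratios would then be checked against the stopping guideline without any new antibody data. Immunogenicity and safety at the same look would also stop at different times.

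**Working it through.** **Inputs**

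- Reference point: the last planned visit of the parent study, Month 14 (SAP 3.1).
- Visits: Month 20, 26, 32, 38, 44 and 50 for Visits 1 to 6 (Protocol Table 2).
- Subjects: up to 90 at each visit (Protocol Tables 4 and 6).
- Assays: four, namely anti-PD, anti-PE, anti-PilA and anti-UspA2 (Protocol Table 5).
- Active-versus-placebo contrasts: two per antigen (SAP 8.2), computed at each visit (SAP 6.2.1).

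**Step 1. Check the period labels.** Elapsed time = cut-off month − 14.

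| Analysis | Cut-off per Protocol 10.9.1 | Months after Month 14 | SAP 8.2 immunogenicity label | Agrees? |
|---|---|---|---|---|
| Interim 1 | Month 20 | 20 − 14 = 6 | six months (Month 20) | yes |
| Interim 2 | Month 26 | 26 − 14 = 12 | one year (Month 26) | yes |
| Interim 3 | Month 38 | 38 − 14 = 24 | one year (Month 26) | **no** |
| Final | Month 50 | 50 − 14 = 36 | every study visit | yes |

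Only the Interim 3 label fails. It is consistent within itself, since Month 26 is indeed one year after Month 14, but it describes Visit 2 under a lead-in that names Visit 4. Period and month must therefore both change.

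**Step 2. Compare the Interim 2 and Interim 3 bullets.** The two immunogenicity descriptions are identical word for word. That suggests the Interim 2 text was carried down. This is an inference about cause, and the contradiction stands without it.

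**Step 3. Look for a deliberate change.** SAP section 9, headed "CHANGES FROM PLANNED ANALYSES", is marked as not applicable, so no departure from the protocol is declared. A later protocol change does not explain it either. For 10.9.1, Protocol Appendix C lists only one added sentence, "Refer to Table 3 for intervals between study visits detailed information", and the Month 38 wording there carries no amendment mark.

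**Step 4. Size of the literal reading.** These are upper limits, assuming 90 subjects and no withdrawals.

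| Quantity | Literal (Visits 1–2) | Intended (Visits 1–4) |
|---|---|---|
| Samples | 2 × 90 = 180 | 4 × 90 = 360 |
| Antibody results | 180 × 4 = 720 | 360 × 4 = 1,440 |
| Active-versus-placebo ratios | 4 × 2 × 2 = 16 | 4 × 2 × 4 = 32 |

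The literal column is exactly the content of Interim 2. The gap between the immunogenicity and safety cut-offs at Interim 3 as written is 38 − 26 = 12 months.

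**The case against.** The strongest reply is that nobody reading the whole section would be misled. The opening sentence and the lead-in carry as much authority as the bullet, and both give Month 38. The bullet also refers to SAP section 6, which covers all six visits and computes ratios at each one. On that view the counts above measure a reading that no one would adopt. Nor is anything lost in the end: the final analysis uses every visit, and the protocol has the earlier analyses reproduced at that stage. The stopping guideline only says that stopping may be considered, the interims are for internal use (SAP Table 2), and SAP section 7 calls all analyses descriptive.

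Most of this stands, and it limits the weight of the point. A programmer would probably use Month 38, and no final estimate, confidence interval or public result depends on the phrase. The counts show the cost of following the bullet literally; they do not predict what will happen. But a clear intent only shows what the correction should be. It does not make the bullet right, and a SAP should not need the protocol to settle which primary-endpoint data enter a planned look.

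**Conclusion.** The Interim 3 immunogenicity cut-off in SAP 8.2 is wrong as written and should be corrected. Three other statements in SAP 8.2 and three in the protocol give Month 38, no change is declared, and the month arithmetic confirms two years. If followed, the bullet would halve the antibody data at this look (at most 720 results instead of 1,440) and leave the stopping guideline with no antibody data beyond Interim 2. Those figures assume full enrolment of 90 and no withdrawals. The practical risk is small because the intent is evident and the guideline is non-binding. No bias or inflation of error rates is claimed.

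**What to change.** In the primary-objective bullet for Interim 3 in SAP 8.2, replace one year (Month 26) with two years (Month 38), so that it matches Protocol 10.9.1 and the Interim 3 lead-in and safety bullet. The identical phrase under Interim 2 is correct and should stay. The cost is one phrase in the SAP, with no new data, no new analysis and no change to the protocol.

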## 3. STUDY DESIGN OVERVIEW

**Figure 1** Study design overview

BS H = blood sample for humoral immune responses;

Rando = randomisation; LV= Last Visit of NTHi-Mcat-001 study; V = Visit of NTHi-Mcat-006 study ; M = Month; VAC = vaccination (indicated in grey);

\* With a cigarette smoking history  $\geq 10$  pack-years (calculation pack-years = average number of cigarettes smoked per day  $\times$  number of years smoked)/20

Protocol waivers or exemptions are not allowed unless necessary for the management of immediate safety concerns. Therefore, adherence to the study design requirements, including those specified in the outline of study procedures (Section 5.5), are essential and required for study conduct.

- Experimental design: Phase I, controlled, multi-centric, single-country, long term follow-up study with three parallel groups from NTHi-Mcat-001 study.
- Duration of the study: For each subject, the study will last approximately 30 months.
- Epoch 001 : Long-term follow-up starting at Visit 1 (Month 20) and ending at Visit 6 (Month 50).
- Primary completion Date (PCD): last subject of Visit 6 (Month 50).

Refer to [glossary of terms](#) for the definition of PCD.

**CONFIDENTIAL**204913 (NTHI-MCAT-006 EXT:001)  
Protocol Amendment 1 Final

- End of Study (EoS): Last testing results released for samples collected at Visit 6.

Refer to [glossary of terms](#) for the definition of EoS.

- Study groups of NTHi-Mcat-001 study:

- **10-10-10-AS:** Up to 30 subjects who have received two doses of the AS01E-adjuvanted GSK Biologicals' NTHi-Mcat investigational vaccine during STEP 2 of NTHi-Mcat-001 study containing 10µg of PD, PE-PilA and UspA2.
- **10-10-3-AS :** Up to 30 subjects who have received two doses of the AS01E-adjuvanted GSK Biologicals' NTHi-Mcat investigational vaccine during STEP 2 of NTHi-Mcat-001 study containing 10µg of PD, 10µg of PE-PilA, and 3.3µg of UspA2.
- **PLACE2 :** Up to 30 subjects who have received two doses of placebo (saline solution) during STEP 2 of the NTHi-Mcat-001 study.

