4.2. Secondary endpoints

- Occurrence of any SAE, during the entire study period in all subjects.
- Occurrence of any pIMD during the entire study period in all subjects.

CONFIDENTIAL204913 (NTHI-MCAT-006 EXT:001)
Statistical Analysis Plan Final

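### SAP 8.2 counts SAEs and pIMDs from Month 14, but all-event collection starts at Visit 1 (Month 20), so the main percentages can mix two capture rules

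*SAP*

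**What the plan says.** **Analysis window.** SAP 8.2 sets the safety data for each of its four steps. All four begin at the parent study's last visit (Month 14). They end at Visit 1, Visit 2, Visit 4 and study end; the final step is "based on safety data collected between last visit in parent study NTHi-Mcat-001 (Month 14) and up to study end".

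**Main table.** SAP 6.3.1 states: "The number and the percentage of subjects who experienced at least one SAE with its exact 95% CI will be tabulated by group" and by preferred term. The same is planned for pIMDs. SAP 11.2.4 uses all enrolled subjects as the denominator and treats a subject with no reported event as event-free.

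**Look-back in the SAP.** The same section says that "SAEs or pIMDs related to the investigational vaccine administered in NTHI-Mcat-001 study, which were reported after last subject last visit of study NTHI-Mcat-001", and after consent to this study, "have to be reported and included in the analyses of NTHI-MCAT-006 study". No separate table is mentioned.

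**Collection.** Protocol 8.2.1 starts SAE and pIMD recording at the first study visit and ends it at study conclusion. For the earlier period it asks, retrospectively, only for vaccine-related SAEs since the end of the primary study. Protocol 5.6.4 sends other conditions from that interval to medical history.

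**Endpoint.** SAP 4.2 has "Occurrence of any pIMD during the entire study period in all subjects", and the parallel wording for SAEs. Protocol 3 places the study epoch between Visit 1 and Visit 6, about 30 months.

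**Interim 1.** Protocol 10.9.1 lists only immunogenicity for the Visit 1 analysis. Protocol 10.9.2 and SAP 8.2 evaluate the secondary (safety) objective there too.

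**The concern.** A percentage of subjects with at least one SAE is read as one occurrence figure over one period. Here the rule for what counts as an event changes part-way through the stated window. Before Visit 1 an event must be judged vaccine-related to enter; after Visit 1 every event enters. The resulting figure is neither an all-event proportion over 36 months nor one over 30 months.

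The final analysis is the one publicly posted (SAP 8.1, Table 2), and a reader of the posting would not see this. Continued pIMD monitoring because of the adjuvant is also a stated reason for the study (protocol 1.2.1), so even a single related event in the gap ought to be identifiable as such.

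There is also a reproducibility problem. The documents give several look-back definitions, so two programmers working from them could include different events.

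**Working it through.** **1. The plan's own figures.** Month 14 to Month 50 is 50 − 14 = 36 months, the 3 years in the secondary objective. Month 20 to Month 50 is 50 − 20 = 30 months, the stated study duration. Both reproduce. The two windows differ by 6 months.

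**2. Share of each SAP 8.2 window before all-event collection**, = 6 / (end month − 14). Months are nominal, since protocol Table 3 treats them as labels.

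| Step | SAP window | Before Visit 1 | All-event part |
|---|---|---|---|
| Interim 1 | 6 months | 6/6 = 100% | 0 months |
| Interim 2 | 12 months | 6/12 = 50% | 6 months |
| Interim 3 | 24 months | 6/24 = 25% | 18 months |
| Final | 36 months | 6/36 = 16.7% | 30 months |

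Interim 1 is not a mixture. Its window holds essentially look-back events only. Mixing arises from Interim 2 onward.

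**3. How one event is handled.**
- Unrelated SAE at Month 17: not collected as an SAE (protocol 8.2.1). The subject counts as event-free (SAP 11.2.4) in a table whose stated window covers Month 17.
- Related SAE at Month 17: collected retrospectively and included.
- Unrelated SAE at Month 21: included.
- Related, non-serious pIMD at Month 17: included by SAP 6.3.1, but protocol 8.2.1 has no retrospective collection for it.

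**4. Look-back start, side by side.**
- SAP 8.2: last parent-study visit, Month 14.
- SAP 6.3.1: parent study's last subject last visit, selected by report date and after consent.
- Protocol 8.2.1: end of the primary study, selected by date of occurrence.

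**5. Effect of one look-back subject with no later event.** 1/30 = 3.3 points; in a group of 20, 1/20 = 5.0 points. Clopper-Pearson 95% intervals for n = 30: 0/30 is 0 to 11.6% and 1/30 is 0.1 to 17.2%; 3/30 is 2.1 to 26.5% and 4/30 is 3.8 to 30.7%.

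**6. Expected shift.** The documents give no event rate. Assume r = 0.05 to 0.15 SAEs per subject-year, with a fraction f = 0.05 to 0.20 judged related. With T years from Visit 1, the all-event proportion is 1 − exp(−rT) and the mixed one is 1 − exp(−rT − 0.5rf).
- Final, T = 2.5: r = 0.05 gives 11.75% against 11.86 to 12.19%; r = 0.15 gives 31.27% against 31.53 to 32.29%. The shift is 0.11 to 1.02 points, or 0.03 to 0.31 subjects per 30.
- Interim 2, T = 0.5: r = 0.05 gives 2.47% against 2.59 to 2.96%; r = 0.15 gives 7.23% against 7.57 to 8.61%. The shift is 0.12 to 1.38 points.

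**The case against.** **The Month 14 start comes from the protocol.** The secondary objective counts from Month 14, and protocol 10.9.1 counts its later safety analyses from the parent study's last visit. This stands, and it rules out reading the SAP window as a plain SAP error. The difficulty is that collection does not support an all-event figure over that window, and the endpoint does not ask for one.

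**The window may be only an outer limit.** SAP 6.3.1 says events are recorded under the protocol's reporting rules. On that reading no unrelated early event is expected. That describes the mixture without removing it.

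**Not all safety counts are affected.** This also stands. SAEs related to participation or concurrent sponsor products are counted "from first visit up to study conclusion will be reported". Deaths, SAE withdrawals and concomitant medication are summarised over the study. The point is confined to the main SAE and pIMD tables. The first-visit count is also not a strict precedent, since no look-back applies to those events.

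**Separation may exist elsewhere.** The list of tables is a separate document not available here, and individual listings are planned at each step. With at most 90 subjects, listings may show these events. The SAP text still does not say what the main percentage contains.

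**Including related events is a defensible safety choice.** Agreed. They should be reported; the question is only whether they belong inside the same percentage.

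**Interim 1** may be an omission in protocol 10.9.1 alone, since 10.9.2 and the SAP agree. It still leaves the protocol inconsistent with itself.

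**Conclusion.** The mismatch is real and in current text. The main by-group SAE and pIMD figures can combine two capture rules and do not correspond to the stated endpoint. The look-back has three different starts and an unsettled position on pIMDs, and Interim 1 safety content is inconsistent.

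It is a minor-to-moderate point. The 0.1 to 1.0 point shift at the final analysis rests entirely on assumed rates and relatedness fractions, and is well inside the width of the exact intervals. The interims are internal, all analyses are descriptive, and the stopping rule uses only GMC ratios.

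Two stronger readings are not supported. A reader might infer a bias between vaccine and placebo, because the protocol's look-back refers to study vaccine and the SAP's to the investigational vaccine. Protocol 4.1 applies the latter term to all three groups, including placebo, so the wording does not establish that placebo events drop out. A reader might also infer from the epoch rule in SAP 11.2.1 that events are wrongly filtered, but no table is stated to use that rule as a filter.

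**What to change.** 1. In SAP 6.3.1 and 8.2, tabulate all SAEs and pIMDs by group from Visit 1 to study conclusion. Beside this, give related look-back events (onset before Visit 1) in a separate by-group table or listing, with a note that only related events were collected before Visit 1. Leave the objective unchanged.
2. Reconcile protocol 8.2.1 with SAP 6.3.1 and 8.2 on a single look-back start, on whether selection is by onset or report date, and on whether related pIMDs are collected retrospectively.
3. Align protocol 10.9.1, protocol 10.9.2 and SAP 8.2 on what safety content Interim 1 has.

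The cost is wording in both documents, one onset-before-Visit-1 flag and one extra table or listing. The drawback is that the main all-event window becomes 30 months instead of 36, and related look-back events sit beside the main percentage instead of inside it. No event is lost.
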